Research question and objectives	
 
Systematic acquisition, analysis and dissemination of information on incidence and prehospital/inhospital course of Purpura fulminans, (possible long-term follow up) and its relation to infectious agents (e.g. meningococcemia, streptococcus etc.)
 
Systematic acquisition, analysis and dissemination of information on current management of PF (sepsis bundles and replacement strategies – protein C, AT, etc.)
 
Systematic acquisition, analysis and dissemination of information on outcomes (morbidity, mortality) of PF with current management strategies, stratified for use or non-use of protein C
 

Design	Prospective multicenter registry derived from systematic data collection on the incidence and treatment of sepsis-associated Purpura fulminans
Population	Patients diagnosed with Purpura fulminans associated with severe sepsis

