### **8.2. Setting**

The registry will include comprehensive records on diagnosis, morbidity and management of SAPF, supplied in the form of eCRFs by the participating centers over a period of three years.

The provision of informed consent by the patient or patient's legal guardian will be required for inclusion in accordance with local legal regulations.

The causal SAPF-inducing pathogen will be identified by microbiological examination.

The presence of Protein C deficiency and its contribution to the clinical manifestations of SAPF will be examined upon enrolment by determinations of Protein C concentration and activity, and subsequently documented in the eCRF. Changes in Protein C levels resulting from supplementation will be monitored as well.

The registry will also compare data on the efficacy of therapeutic approaches including or omitting Protein C supplementation.

A further aspect of specific interest is the stratification of outcomes by demographic (e.g. age, sex) and clinical criteria (e.g. morbidity at admission, causal pathogen), in order to identify subgroups of patients with above-average or marginal responsiveness to Protein C supplementation.

The contribution of supportive measures (e.g. assisted ventilation, renal replacement therapy, fluid resuscitation) and co-medication (e.g. vasopressors, corticosteroids, heparin etc.) will be evaluated as well.

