**Flowchart**

Activity / Endpoint	Baseline 	Post-diagnosis period (days)					End of study at hospital discharge or in-hospital death after ICU discharge
		1	3	5	7	ICU discharge or death on ICU after day 7	
Confirm inclusion criteria	x						
Provision of informed consent 	x						
Demographic data collection (incl. ethnic origin)	x						
Risk factors (vaccination status, asplenia) and comorbidities	x						
Estimated time of SAPF onset (hours)	x						
Mortality prediction (APACHE II/SAPS II  or PRISM III  score)	x						
Morbidity assessment (SOFA  /PELOD  score)	x	x	x	x	x		
Laboratory parameters (hematology, coagulation, inflammation)	x	x	x	x	x		
Purpura lesion assessment (c.f. eCRF)	x	x	x	x	x		
Vasopressor use record	x	x	x	x	x	x	
Site, source and origin of infection (including viral)							x
Concomitant causal, supportive and adjunctive treatment (c.f. eCRF)		x	x	x	x	x	
Cumulative dose of blood products and anti-coagulant treatment		x	x	x	x	x	
Antimicrobials		x	x	x	x	x	
Days in ICU							x
Days on mechanical ventilation							x
ECMO and circulatory support systems		x	x	x	x	x	
Days/type on renal replacement therapy							x
Purpura-related surgery (fasciotomy, debridement, amputation)							x
In-hospital mortality assessment		x	x	x	x	x	x
Days in hospital							x
Adverse drug reactions							x

 admission at ICU; according to local regulations APACHE II/SAPS II and SOFA scores will be used in patients aged above 16 PRISM III and PELOD scores will be used in patients aged below 16

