### 8.3. Variables

The selection of the endpoint all-cause in-hospital mortality is justified, in view of the exceptional severity of the disease *per se* and considerable risk associated with the subsequent management of its late sequelae (e.g. reconstructive surgery). On a case-by-case basis, a comparison with the probability of a lethal outcome, as defined by the APACHE II/ SAPS II or PRISM III score, will be made.

Changes in morbidity (as assessed by the SOFA or PELOD indices) will be presented by the difference between scores measured at admission and after 1, 3, 5 and 7 days upon being diagnosed with SAPF ( $\Delta$ SOFA, dPELOD), as well as by the mean total score (SOFA, PELOD) recorded over the observation period of 7 days.

Records will also include description of imminent surgical interventions (during the SAPF treatment), as well as reconstructive measures (skin grafting, amputation).

The sepsis-inducing pathogen and the primarily affected organ will be identified by the results of microbiological examinations and in accordance with clinical manifestations.

Further endpoints comprise the length of stay in the ICU and the total duration of hospitalization (including time of post-SAPF therapy).

Changes in hematological, coagulation and inflammatory parameters will be monitored at selected intervals across the treatment and serve as biomarkers of treatment efficacy or surrogate endpoints, as follows:

- Thrombocyte counts
- Leukocyte counts
- Hemoglobin
- Prothrombin time (PT)
- Activated partial thromboplastin time (aPTT)
- Fibrinogen
- D dimers
- Thrombin-Antithrombin complex (TATc)
- Protein C activity
- Antithrombin III activity
- C-reactive protein (CRP)
- Procalcitonin (PCT)
- Interleukin 6 (IL-6)

Several of these parameters have been used in clinical studies and shown significant changes in the course of therapeutic interventions in sepsis and Purpura fulminans [Bernard et al., 2001; de Kleijn et al., 2003; Schellongowski et al., 2006; Shorr et al., 2008].

Laboratory indices of organ dysfunction are confined to measurements of

- Glucose
- Lactate
- Creatine kinase

Recording of adverse events related to the treatment of SAPF is left at the discretion of the local site investigator (c.f. comment in 9.9. *Limitations of research methods*); the emphasis is laid on

- bleeding incidents
- thrombotic events

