#### 8.4. Data sources

Registry subjects will be identified by the participating centers. The recruitment will be primarily based on the concomitant presence of clinical signs of sepsis and *Purpura fulminans*. Clarification of the underlying etiopathogenesis will be performed *post hoc*, upon collection of additional clinical and laboratory data.

Data capture comprises assessment at baseline and at several intervals of 24 (initially) and 48 (subsequently) hours for an overall period of 7 days, while in ICU. A final appraisal of the patient's status will take place at the time point of discharge from the hospital.

The exposure to individual therapeutic agents will be deduced from doses and frequency of application during the period spent in ICU.

The influence of potential confounding variables and effect modifiers (e.g. concomitant anticoagulant medication, fluid resuscitation, renal replacement therapy etc.) will be extrapolated from the corresponding specific entries in the eCRF.

The outcome indicators have been previously validated and are routinely used.

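### Exposure is taken only from the ICU stay and pre-ICU treatment is not specified for recording, so some Protein C users may be misclassified and baseline values may already be treated

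*Combined protocol and SAP*

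**What the plan says.** The first objective in the abstract (section 4) is to collect "information on incidence and prehospital/inhospital course of" Purpura fulminans. Sections 8.1 and 8.7 put the emphasis on comparing outcomes with and without Protein C, using logistic regression for in-hospital mortality. Severity score, laboratory values and co-medication are among the possible covariates.

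Section 8.4 sets the exposure rule: "The exposure to individual therapeutic agents will be deduced from doses and frequency of application during the period spent in ICU". It limits interval data collection in the same way: "Data capture comprises assessment at baseline and at several intervals of 24 (initially) and 48 (subsequently) hours for an overall period of 7 days, while" the patient is in ICU. Footnote 1 of the flowchart in 8.2 defines baseline as "admission at ICU".

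The flowchart rows "Concomitant causal, supportive and adjunctive treatment (c.f. eCRF" and "Cumulative dose of blood products and anti-coagulant treatment", and those for antimicrobials and for ECMO and circulatory support, have no baseline mark and start at day 1. The vasopressor row is marked at baseline. Section 8.2 adds that Protein C deficiency, and its contribution to the clinical picture, "will be examined upon enrolment by determinations of Protein C concentration and activity". Section 8.6 says that data are collected in accordance with the flowchart. The limitations in 8.9 do not mention treatment before ICU.

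**The concern.** Section 6 describes a rapidly evolving disease, and section 9 ties eligibility for treatment to manifest clinical signs, not to ICU admission. Antimicrobials, plasma or Protein C can therefore be started in an emergency department, on a ward or at a referring hospital. If the plan does not ask for this, three things are at stake:

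- **Exposure.** The with/without Protein C grouping may be wrong for some patients.
- **Baseline.** A partly corrected Protein C level cannot be told from an untreated one, and the severity score used for adjustment may already reflect treatment.
- **Confounding.** Pre-ICU antimicrobials and plasma are not available as covariates, although 8.9 itself says that efficacy has to be judged together with co-medication.

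**Working it through.** The plan gives no figure to reproduce here. The check is a reading of the flowchart against 8.4, followed by two illustrations on assumed inputs.

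**Step 1: the flowchart rows.**

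| Row | Baseline | Days 1, 3, 5, 7 | ICU discharge or death | End of study |
|---|---|---|---|---|
| Vasopressors | x | x | x | |
| Concomitant treatment; blood products and anticoagulants; antimicrobials; ECMO | | x | x | |
| Ventilation, renal replacement, purpura-related surgery | | | | x |
| Onset time; risk factors and comorbidities | x | | | |
| Site and source of infection; days in ICU; days in hospital | | | | x |

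Onset time gives the length of the interval before ICU, but not what was done in it. Days in hospital minus days in ICU mixes ward time before and after the ICU.

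**Step 2: how 8.4 classes patients.**

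- Protein C started before ICU and continued there: user, correctly.
- Protein C given only before ICU: non-user, wrongly.
- Plasma only, before ICU: non-user of Protein C, correctly, but the plasma is an unrecorded confounder and can alter the baseline Protein C level.
- Antimicrobials before ICU: no effect on the grouping, but not available for adjustment.

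**Step 3: misclassification (assumed inputs).** Let Nt and Nu be the true users and non-users, pt and pu their mortality, and m the share of users dosed only before ICU. Assume those patients have mortality pt. Observed non-user mortality is (Nu·pu + m·Nt·pt)/(Nu + m·Nt). The total of 150 follows from the abstract (50 per year × 3 years). The split, the mortality rates and m are assumptions.

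With Nt = 60, Nu = 90, pt = 40%, pu = 55%:

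- m = 10%: (49.5 + 2.4)/96 = 54.1%, difference 14.1 points
- m = 20%: (49.5 + 4.8)/102 = 53.2%, difference 13.2 points
- m = 30%: (49.5 + 7.2)/108 = 52.5%, difference 12.5 points

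The true difference is 15 points.

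With Nt = Nu = 75, pu = 50%, and a two-sided 0.05 test of two proportions:

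| m | pt = 30%: odds ratio, power | pt = 40%: odds ratio, power |
|---|---|---|
| 0 | 0.43, 71% | 0.67, 23% |
| 10% | 0.46, 62% | 0.69, 20% |
| 20% | 0.49, 53% | 0.71, 17% |
| 30% | 0.52, 45% | 0.73, 14% |

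The shrinkage depends on the assumption that pre-ICU-only users die at the same rate as other users. If they died more often than true non-users, for instance because early death cut treatment short, the observed difference would grow instead.

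**Step 4: unrecorded confounding (assumed inputs).** Take mortality of 40% with and 60% without pre-ICU antimicrobials, and no Protein C effect.

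- 60% of users and 50% of non-users had them: 0.6×40 + 0.4×60 = 48% against 0.5×40 + 0.5×60 = 50%, a spurious 2 points.
- 70% against 40%: 0.7×40 + 0.3×60 = 46% against 0.4×40 + 0.6×60 = 52%, a spurious 6 points.

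These are unadjusted. Adjustment for baseline severity would remove part of the difference to the extent that the score carries the same information.

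**The case against.** The strongest reply is that the eCRF may already ask for these data. The treatment row refers to it, 8.4 says that confounders come from specific eCRF entries, and 8.9 promises to consider co-medication in its design. A cumulative dose recorded at day 1 could also include earlier doses, and the day columns count from diagnosis, not from ICU admission (8.3: "difference between scores measured at admission and after 1, 3, 5 and 7 days upon being diagnosed with SAPF"). This stands as far as it goes: the documents support saying that pre-ICU treatment is not specified, not that it is lost. It does not remove the point, because the 8.4 exposure sentence is explicit and 8.6 ties collection to the flowchart. If the eCRF does collect it, 8.4 still needs correcting.

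A reader might also infer more than the documents support:

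- **That all treatment is recorded only from day 1.** Vasopressors are marked at baseline, and several supportive measures are totalled at end of study. The day-1 record may also cover early ICU care, so the missing baseline marks matter less than the ICU-only window.
- **That the prehospital objective cannot be answered at all.** Onset time, vaccination status, asplenia and comorbidities serve it in part. The wording appears only in the abstract, not among the aims in section 7, and emergency department and ward care are in-hospital.
- **That patients given plasma only are misclassified.** They are correctly non-users of Protein C.
- **That early treatment is shown to matter most for prognosis.** Section 6 says only that the disease evolves rapidly.

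**Conclusion.** The point holds as a gap in specified data capture. The ICU-only exposure rule would class patients given Protein C solely before ICU as non-users. It leaves the treatment status of baseline scores and laboratory values unidentified, and leaves the mortality model without pre-ICU antimicrobials or plasma as covariates. For the time before ICU, the course objective rests on onset time and background risk factors.

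The size is unknown, since the documents do not say how often Protein C is given only before ICU or how early care differs between the groups. On the assumed inputs, misclassification is modest on the difference scale (15 down to 12.5 points at 30%), and confounding of 2 to 6 points is possible. A reader might take these figures as an estimate of bias in this registry. They are not: they show what the plan leaves unmeasured. The conclusion rests on the protocol text and would soften if the eCRF records earlier treatment.

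**What to change.** 1. In 8.4, replace the ICU-only limit in the exposure sentence with a window from first medical contact for the current sepsis episode (or SAPF onset, if earlier) to ICU discharge. Starting at SAPF onset alone would miss antimicrobials given for sepsis before purpura appeared.
2. Add a Baseline entry to the flowchart rows for concomitant treatment, blood products and anticoagulants, and antimicrobials. Record agent, first start date and time, and place (prehospital, emergency department, ward, referring hospital), with an unknown option.
3. Flag baseline laboratory samples as taken before or after the first plasma, Protein C or antithrombin dose, and report baseline Protein C deficiency separately for the samples taken before.
4. Where earlier care cannot be recovered for patients already entered, say so in 8.9. Section 9 has patient numbers replaced after data verification so that identity cannot be traced, so late retrieval may not be possible.

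The cost is a few extra eCRF fields across about 30 centers that have no default monitoring visits (8.8). Records from referring hospitals will be incomplete for some patients. Patient care is unaffected.

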## **10. Management and reporting of adverse events/adverse reactions**

Considering the critical condition of patients with Purpura fulminans and their high disease-related mortality, the documentation and reporting of all adverse events (AE) and serious adverse events (SAE) occurring in these patients is beyond the scope of this registry.

In view of the complex pathology and the multitude of concomitantly used therapeutic agents in SAPF patients, registration of treatment-emergent adverse drug reactions (ADR) will be confined to those, which denote pathological alteration of the coagulation status. In this context, ADR of specific interest include

- bleeding (especially intracranial and in visceral organs)
- thrombotic events

Occurrence of adverse drug reactions (ADR) will be recorded by the study teams at the participating centers in the eCRF, with the local investigator being responsible for the assessment of the ADR. Severity of ADR will be assessed by means of a three-grade-scale (mild-moderate-severe). In view of the severity of the condition, however, it is predictably difficult to discern ADR of mild and moderate intensity.

Additionally an ADR Report Form for these assessments will be distributed to the local investigators as a part of the Investigator Site File (ISF). Documented treatment-related ADR or other safety

concerns (regardless of the expectedness or causality) will be forwarded by the local investigator by his own responsibility to the Marketing Authorization Holder of the presumably involved product and the Advisory Committee of the registry within 24 hours of awareness.

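### ADRs have no stated end before hospital discharge, but drug exposure is recorded only to ICU discharge, so ward-phase ADRs cannot be related to concurrent treatment

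*Combined protocol and SAP*

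**What the plan says.** **Exposure.** Section 8.4 states: "The exposure to individual therapeutic agents will be deduced from doses and frequency of application during the period spent in ICU". In the flowchart (section 8.2), the row "Cumulative dose of blood products and anti-coagulant treatment" is marked at days 1, 3, 5 and 7 and at ICU discharge or death on ICU after day 7. It has no mark in the final column. The row for concomitant treatment has the same pattern.

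**ADRs.** The flowchart row "Adverse drug reactions" has a single mark, in the column headed "End of study at hospital discharge or in-hospital death after ICU discharge". Section 10 adds that "registration of treatment-emergent adverse drug reactions (ADR) will be confined to those, which denote pathological alteration of the coagulation status", names bleeding and thrombotic events as of specific interest, and makes the local investigator responsible for assessing each ADR. It gives no end date for ADR recording.

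**After ICU.** The only post-ICU contact in 8.4 is this: "A final appraisal of the patient's status will take place at the time point of discharge from the hospital". No section provides for a record of treatment given on the ward.

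**Analysis.** Section 8.7 specifies models for mortality and for the organ-failure scores. ADRs fall under its general provisions: descriptive statistics for all endpoints, and between-group comparisons by parametric or non-parametric tests. No ADR risk window or rule linking an ADR to exposure is given.

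**The concern.** The numerator and the exposure that should explain it have different windows. Between ICU discharge and the end of hospital stay, an ADR can be entered while the drugs given at that time are not. Section 8.9 expects the post-ICU period to vary widely between patients and to include reconstructive surgery, so the unmatched interval is not negligible for everyone.

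Two consequences follow, and they are separate problems.

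- **Attribution.** The only exposure on file for a ward ADR is ICU exposure. A table of ADRs by Protein C use would set ward events against a treatment that may have ended earlier, with no record of the anticoagulants in use when the event occurred. Section 8.4 itself names concomitant anticoagulants as a potential confounder to be taken from eCRF entries. For the ward phase the flowchart schedules no such entries.
- **Time at risk.** A patient who dies in ICU has no ward phase. A group with better ICU survival collects more ward ADRs even if no treatment differs in safety.

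Bleeding and thrombosis are the only adverse events named among the endpoints in the abstract. Section 11 says that safety records, with the biannual evaluations, will feed the therapy recommendations sent to centres.

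**Working it through.** **Step 1: compare the windows.** The plan gives no figure to reproduce, so this is a column-by-column reading of the flowchart.

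| Item | Days 1, 3, 5, 7 | ICU discharge or death on ICU | End of study |
|---|---|---|---|
| Concomitant treatment | marked | marked | – |
| Blood products and anticoagulants | marked | marked | – |
| Adverse drug reactions | – | – | marked |

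Section 8.6 says data are collected according to the flowchart, so this layout governs the eCRF. The unmatched interval runs from ICU discharge to hospital discharge or in-hospital death. Neither its length nor the number of ADRs in it can be derived from the documents.

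**Step 2: how survival enters a crude count.** Let r_I be the ADR risk in ICU, r_W the ward ADR risk in an ICU survivor, and S the ICU survival. All are assumptions; the protocol gives no ADR rates. Suppose treatment affects neither risk. Then

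expected ADRs per 100 patients = 100 × (r_I + S × r_W).

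Take r_I = 10% and S = 60% in one group, 40% in the other.

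| r_W | S = 60% | S = 40% | Ratio | Ward share of ADRs |
|---|---|---|---|---|
| 5% | 10 + 3 = 13 | 10 + 2 = 12 | 1.08 | 3/13 and 2/12 |
| 15% | 10 + 9 = 19 | 10 + 6 = 16 | 1.19 | 9/19 and 6/16 |
| 30% | 10 + 18 = 28 | 10 + 12 = 22 | 1.27 | 18/28 and 12/22 |

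With survival of 55% versus 45% and r_W = 15%, the counts are 18.25 and 16.75, a ratio of 1.09. With equal survival the ratio is 1 whatever the ward risk.

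**Step 3: scale.** The abstract's 50 patients a year for 3 years gives 150. Split evenly (an assumption), 75 per group at 19 and 16 per 100 gives 14.25 and 12 ADRs, a difference of about two events.

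**Step 4: what each problem needs.** The ratios in step 2 come from unequal time at risk, not from missing exposure, so recording ward drugs would not change them. The ward share in the last column is the part that has no concurrent exposure record. Restricting to ICU-phase onset removes that part, but early ICU deaths still contribute fewer ICU days, so a time-based denominator is needed as well.

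**The case against.** **The single mark may not show ward surveillance.** The same column holds days in ICU, days on ventilation and the site of infection, which are closing entries largely about the ICU phase. The ADR mark may likewise be a cumulative entry made at discharge. This is fair: the mark fixes when the form is completed, not the risk period. But no section ends the ADR period earlier, so ward ADRs can enter.

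**Only assessed reactions enter.** A reader might infer that every ward bleed or thrombosis is counted against Protein C. The documents do not support that. An event must be judged a treatment-related ADR by the local investigator, and section 10 provides a separate report form that goes to the marketing authorisation holder of the product presumed to be involved. A ward anticoagulant can therefore be named as the suspect. The eCRF and the form are not in the documents and may already hold onset date and product. This can help attribute a single case. It does not show how many patients received anticoagulants on the ward, and it does not equalise observation time.

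**No ADR comparison by Protein C is specified.** This is correct. The abstract's stratified objective covers morbidity and mortality, and 8.5 says dichotomisation might be required and might suit only selected endpoints. Such a table is possible under the general wording of 8.7, not prescribed by it.

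**The ward phase is not said to be long.** Section 8.9 says post-ICU recovery varies; it gives no expected length.

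**ADRs in ICU deaths.** Read literally, the heading of the last column leaves out patients who die in ICU, and a reader might infer that their ADRs are never recorded. Section 10 contains no such exclusion: "Occurrence of adverse drug reactions (ADR) will be recorded by the study teams at the participating centers in the eCRF". This is more likely a matter of layout, and the point does not rely on it.

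**Conclusion.** The mismatch stands and follows from stated rules: 8.4 and the flowchart end exposure at ICU discharge, while the ADR entry is at the end of hospital stay with no earlier cut-off. Ward-phase ADRs cannot be related to concurrent anticoagulant, blood-product or Protein C exposure from registry data, and nothing prevents their being tabulated by ICU treatment.

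Crude ADR counts by treatment group also depend on survival. The size is unknown. Ratios of about 1.08 to 1.27 hold only under the assumed ICU risk of 10%, survival of 60% versus 40% and ward risks of 5% to 30%; they shrink with a smaller survival gap and vanish when survival is equal. They show a direction and are not estimates for this registry.

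This is a correctable weakness in the safety data. It does not show that any treatment will be wrongly blamed, and it does not touch the mortality or organ-score analyses.

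**What to change.** Choose one of two routes.

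1. Mark the end-of-study column for the blood-product and anticoagulant row, restricted to anticoagulants, blood products and Protein C given on the ward.
2. State in 8.7 that any ADR comparison between treatment groups uses only events with onset up to ICU discharge.

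In either case:

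- make sure that ADR onset date and suspected product are in the eCRF;
- report ICU-phase and ward-phase ADRs separately;
- give ADRs per patient-day at risk within each phase. Days in ICU and days in hospital are already collected, but ward days should count only time after ICU discharge, since the hospital total may include days before ICU admission.

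Route 1 costs a short extra entry at the existing discharge contact. Route 2 costs one sentence in the analysis section and leaves fewer events in the exposure-linked comparison. Onset date and suspected product cost nothing if the forms already hold them. Neither route changes patient care. The entry is best added prospectively, because section 9 foresees replacing patient numbers so that identities cannot be traced, after which ward exposure may not be recoverable.
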